APPENDIX E: New York Heart Association Classifications

Clinical Evaluation of Functional Capacity of Patients With Heart Disease in Relation to Ordinary Physical Activity

Class	Cardiac Symptoms	Limitations	Need for Additional Rest*	Physical Ability to Work**
I	None	None	None	Full Time
II	Only moderate	Slight	Usually only slight or occasional	Usually full time
III	Defined, with less than ordinary activity	Marked	Usually moderate	Usually part time
IV	May be present even at rest, and any activity increases discomfort	Extreme	Marked	Unable to work

* To control or relieve symptoms, as determined by the patient, rather than as advised by the physician

** At accustomed occupation or usual tasks

APPENDIX F: Medications that May Cause QTc Prolongation

This table lists drugs that may prolong the QT_c interval. Cediranib may be administered after a 5 half-life washout period elapses following discontinuation of prohibited drugs. Drugs labeled “Use discretion” may be co-administered in the absence of other risk factors and with appropriate monitoring. Drugs with a weak association may be administered at usual doses with appropriate monitoring.

Compound	Compound Half Life	QTc Prolongation Association/ Concurrent Administration	Possible Washout Period – Hours	Possible Washout Period - Days
Alfuzocin	~10 hours	Some/Use Discretion		7
Amantadine	17 +/- 4 hours (10-25)	Some/Use Discretion		4
Amiodarone (cordarone)	58 days (15-142) 36 days (active metabolite)	Strong/Prohibited		180
Amitriptyline*	> 24 hours, wide interpatient variability	Weak/At usual doses		
Amoxapine	~ 8 hours	Weak/At usual doses	40 hours	2 days
Ampicillin	1 to 1.5 hours	Weak/At usual doses		
Arsenic trioxide	Not characterized; may be weeks	Strong/Prohibited		
Azithromycin	40 hours	Some/Use Discretion		
Bepidil	42 hr (26-64)	Strong/Prohibited		10
Chloral hydrate	Readily converted to Trichloroethanol (active metabolite T _{1/2} =7-10 hour)	Some/Use Discretion	48	
Chloroquine	6 to 60 days; mean 20 days	Strong/Prohibited		
Chlorpromazine	30 +/- 7 hours	Strong/Prohibited		7
Ciprofloxacin	3.5 to 4.5 hours	Weak/At usual doses		
Cisapride	6 – 12 hour, up to 20 hour	Strong/Prohibited	60	
Citalopram		Weak/At usual doses		
Clarithromycin	Non linear PK3-4 hr	Strong/Prohibited	36	3

	(250mg Q12)			
	5-7 hr (500mg Q12)			
Clomipramine	~ 21 hours	Weak/At usual doses		
Clozapine	12 hours at steady state	Some/Use Discretion		
Desipramine*	> 24 hours, wide interpatient variability	Weak/At usual doses		
Disopyramide	6.7 hr (4-10)	Strong/Prohibited	36	
Dofetilide	10 hr	Strong/Prohibited	48	
Dolesetron	8.1 hr	Some/Use Discretion		
Domperidone	7-8 hr	Strong/Prohibited	48	
Doxepin*	> 24 hours, wide interpatient variability	Weak/At usual doses		
Droperidol	2.2 hours	Strong/Prohibited	10	
Erythromycin	* Each salt form has different Half life*	Strong/Prohibited		
Felbamate	20-23 hr	Some/Use Discretion		5
Flecainide	20 hr (12-27)	Some/Use Discretion		5
Fluconazole	~ 30 hours	Weak/At usual doses		
Foscarnet	87.5+/-41.8 hours *distribution and release from bone*	Some/Use Discretion		20
Fosphenytoin	12-29 hr	Some/Use Discretion		6
Galantamine		Weak/At usual doses		
Gatifloxacin	7-14 hr	Some/Use Discretion	48	
Gemifloxacin	7 hours	Some/Use Discretion	48	
Granisetron	3 to 4 hours	Some/Use Discretion		
Grepafloracin	16 hr	Some/Use Discretion		3
Halofantrine	6-10 days (variable among individual)	Strong/Prohibited		45
Haloperidol	18 +/-5 hr	Strong/Prohibited		5
Ibutilide	6 hours (2-12) * variable among subject*	Strong/Prohibited	36	3
Imipramine*	> 24 hours, wide	Weak/At usual		

	interpatient variability	doses		
Indapamide	14 hours (biphasic elimination)	Some/Use Discretion		3
Isradipine	8 hours (multiple metabolites)	Some/Use Discretion	48	
Itraconazole	20 hours, increasing to 40 hours	Weak/At usual doses		
Ketoconazole	2 hours, increasing to 8 hours	Weak/At usual doses		
Levofloxacin	6-8 hours	Some/Use Discretion	48	
Levomethadyl	Multiple compartment PK with active metabolite 2.6 day for LAAM, 2 day for nor-LAAM, 4 day for dinor-LAAM	Strong/Prohibited		20
Lithium	24 hour (10-50)	Some/Use Discretion		7
Mefloquine	13 to 24 days	Weak/At usual doses		
Mesoridazine	24-48 hours (animal study)	Strong/Prohibited		10
Methadone	15-30 hours	Strong/Prohibited		7
Mexiletine	>10 hours	Weak/At usual doses		
Moexipril/HCTZ	2-9 hour (include active metabolite) for moexipril; 5.6-14.8 hours for HCTZ	Some/Use Discretion	48	
Moxifloxacin	12 +/-1.3 hours	Some/Use Discretion	72	
Naratriptan	6 hours		36	
Nicardipine	~ 2 hour post IV infusion	Some/Use Discretion	12	
Nortriptyline*	> 24 hours, wide interpatient variability	Weak/At usual doses		
Octreotide	1.7 hours	Some/Use Discretion	12	
Ofloxacin	5 to 7.5 hours	Some/Use Discretion		2
Ondansetron	4 hours (IV/IM); 3 hours (PO)	Some/Use Discretion		1 to 3
Paroxetine		Weak/At usual doses		
Pentamidine	6.4+/-1.3 hours	Strong/Prohibited	36	
Pimozide	55 hours	Strong/Prohibited		10

Procainamide	3-4 hour for PA and NAPA (active metabolite)	Strong/Prohibited	24	3
Protiptyline*	> 24 hours, wide interpatient variability	Weak/At usual doses		
Quetiapine	6 hours	Some/Use Discretion	36	
Quinidine	6-8 hours in adult; 3-4 hours in children	Strong/Prohibited	36	
Quinine	4-5 hours	Weak/At usual doses		
Risperidone	3-20 hours (extensive to poor metabolizer) 9-hydroxyrisperidone (active metabolite) T _{1/2} =21-30 hours (extensive to poor metabolizer)	Some/Use Discretion		4
Roxithromycin		Some/Use Discretion		
Salmeterol	5.5 hours (only one datum)	Some/Use Discretion	36	
Sertraline	~ 26 hours	Weak/At usual doses		
Solifenacin	40 to 68 hours	Weak/At usual doses		
Sotalol	12 hours	Strong/Prohibited	72	
Sparfloxacin	20 hours (16-30)	Strong/Prohibited		4
Sumatriptan	2.5 hours		12	
Tacrolimus	~34 hours in healthy; ~19 hours in Kidney transplant	Some/Use Discretion		7
Tamoxifen	5-7 days (biphasic)	Some/Use Discretion		30
Telithromycin	2-3 hr	Some/Use Discretion	24	
Thioridazine	20-40 hours (Phenothiazines)	Strong/Prohibited		7
Tizanidine	2.5 hours	Some/Use Discretion	12	
Trimethoprim/sulfa	6 to 17 hours	Weak/At usual doses		
Trimipramine	~ 23 hours	Weak/At usual doses		
Vardenafil	4 to 5 hours	Some/Use Discretion		

Venlafaxine	5 +/-2 hours for parent comp. 11 +/-2 hours for OVD (active metabolite)	Some/Use Discretion	60	
Voriconazole	6 hours; dose dependent	Some/Use Discretion		
Ziprasidone	7 hr	Some/Use Discretion	36	
Zolmitriptan	2.8-3.7 hours (higher in female)	Weak/At usual doses	18	

*** These agents are tricyclic antidepressants; traditionally, they have only been associated with QTc interval prolongation at serum levels approaching or into the range of toxicity. Special caution is advised in the elderly and children/adolescents.**

References:

1. Physician's Desk Reference 2002
2. Facts and Comparisons (update to June 2005)
3. The Pharmacological Basis of Therapeutics 9th Edition, 1996
4. ArizonaCERT Center for Education and Research on Therapeutics, <https://www.crediblemeds.org/index.php>

Disclaimer: This chart was updated on August 23, 2005. It may not include all drugs associated with QTc prolongation. Prescribers are advised to do further research if they have additional questions.

DFCI IRB Protocol # 09-293

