3.2. Exclusion Criteria

Participants who exhibit any of the following conditions at screening will not be eligible for admission into the study.

- 3.2.1.** Participants who have had chemotherapy or radiotherapy within 3 weeks (6 weeks for nitrosoureas or mitomycin C) prior to entering the study or those who have not recovered from adverse events due to agents administered more than 3 weeks earlier.
- 3.2.2.** Participants may not be receiving any other investigational agents nor have participated in an investigational trial within the past 4 weeks. Subjects may not have received prior treatment affecting the VEGF pathway in the recurrent setting, including thalidomide, bevacizumab, sunitinib, or sorafenib. In the Phase I portion of the trial, subjects may not have received prior treatment with oregovomab (OvaRex) or any other antibodies that may interfere with CA-125 measurements.
- 3.2.3.** Patients with untreated brain metastases, spinal cord compression, or evidence of symptomatic brain metastases or leptomeningeal disease as noted on CT or MRI scans should not be included on this study, since neurologic dysfunction may confound the evaluation of neurologic and other adverse events. Screening imaging to rule out brain metastases is not required for screening, but should be performed prior to study enrollment if clinically indicated. Patients with treated brain metastases and resolution of any associated symptoms must demonstrate stable post-therapeutic imaging for at least 6 months following therapy prior to starting study drug.
- 3.2.4.** History of allergic reactions attributed to compounds of similar chemical or biologic composition to cediranib or olaparib.
- 3.2.5.** Participants receiving any medications or substances that are *strong* inhibitors or inducers of CYP3A4 are ineligible. A list of CYP3A4 inhibitors and inducers is provided in Appendix D. Dihydropyridine calcium-channel blockers are permitted for management of hypertension.
- 3.2.6.** Patients with any of the following:
- History of myocardial infarction within six months
 - Patients with QTc prolongation > 500 msec or other significant ECG abnormality noted within 14 days of treatment.
 - For patients enrolled in the Phase 1-T portion of the protocol, the QTc should not exceed 470 msec.
 - NYHA classification of III or IV

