 - If cardiac function assessment is clinically indicated or performed: LVEF less than normal per institutional guidelines, or < 55%, if threshold for normal not otherwise specified by institutional guidelines.
 - Condition requiring concurrent use of drugs or biologics with pro-arrhythmic potential (see Appendix F).

- 3.2.7.** History of stroke or transient ischemic attack within six months.
- 3.2.8.** Patients may not have any evidence of pre-existing inadequately controlled hypertension (defined as a systolic BP of >140 mmHg or a diastolic BP of >90 mmHg), and must have a normal blood pressure (\leq 140/90 mmHg) taken in the clinic setting by a medical professional within 2 weeks prior to starting study. Patients with hypertension may be managed with up to a maximum of three antihypertensive medications. Patients who are on three antihypertensive medications must be actively followed by a cardiologist or blood pressure specialist for management of blood pressure while on protocol.
- 3.2.9.** Any prior history of hypertensive crisis or hypertensive encephalopathy
- 3.2.10.** Clinical significant peripheral vascular disease or vascular disease (aortic aneurysm or aortic dissection)
- 3.2.11.** Unstable angina
- 3.2.12.** Major surgical procedure, open biopsy, or significant traumatic injury within 28 days prior to starting cediranib.
- 3.2.13.** History of abdominal fistula, gastrointestinal perforation or intra-abdominal abscess.
- 3.2.14.** Current signs and/or symptoms of bowel obstruction or signs and/or symptoms of bowel obstruction within 3 months prior to starting study drugs.
- 3.2.15.** Current dependency on IV hydration or TPN.
- 3.2.16.** Evidence of coagulopathy or bleeding diathesis. Therapeutic anticoagulation for prior thromboembolic events is permitted.
- 3.2.17.** Uncontrolled intercurrent illness including, but not limited to ongoing or active infection, symptomatic congestive heart failure, unstable angina pectoris, cardiac arrhythmia, or psychiatric illness/social situations that would limit compliance with study requirements.

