- j: ECG done prior to Cycle 1 and 2, and then prior to every cycle if clinically indicated. The pre-study ECG may be used as the Cycle 1 ECG if performed within 7 days of Cycle 1 Day 1.
- k: MUGA or echocardiogram should be done at baseline and every 4 cycles for those patients at increased risk for compromised LVEF. Increased risk patients have had one or more of the following: (1) prior treatment with anthracyclines, (2) prior treatment with trastuzumab, (3) NY Heart Association classification of II, (4) prior central thoracic RT, (5) history of myocardial infarction within the 12 months prior.
- l: beta-HCG for women of childbearing potential.
- m: Tumor measurements by CT scans or MRI will be performed within the 4 weeks prior to starting cediranib/olaparib and will be performed after every 8 weeks (+/- 1 week) of treatment. If a partial or complete response is noted, a confirmatory CT scan or MRI should be performed. The next planned restaging CT scan or MRI may be used as the confirmatory scan. For patients in the Phase 2 portion of the trial, the frequency of restaging studies will decrease to once every 12 weeks (+/- 1 week) after the 20th cycle of treatment.
- n: The Family Risk Assessment questionnaire (Appendix I) should be completed by the patient and returned to the study staff by Cycle 2.
- o: For patients opting to participate in translational studies at the NCI. Study schedules will be as per Section 5.1.4.
- p: Off-treatment assessments should be performed within 30 days of stopping study treatment.
- q: For patients in the Phase 2 portion of the trial who have been on trial for greater than 4 years without evidence of disease progression, the treating investigator may choose to decrease the frequency of re-staging CT scans to once every 4 cycles.
- r: For patients in the Phase 2 portion of the trial who have been on trial for greater than 4 years without evidence of disease progression, the treating investigator may choose to decrease the frequency of visits to once every 2 cycles. These patients should have CBC with differential, serum chemistry, and urine protein assessment (UPC or urinalysis) performed and con-meds, adverse events, and blood pressure diary should be reviewed in-person or by telephone with the study team, but all other assessments may be omitted.

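### Appendix F requires a 5 half-life washout of prohibited QT drugs, but its 180-day amiodarone entry covers only 3.1 half-lives of the parent drug; pimozide falls short by less

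*Combined protocol and SAP*

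**What the plan says.** Appendix F opens with the condition for starting cediranib after a prohibited drug has been stopped: "Cediranib may be administered after a 5 half-life washout period elapses following discontinuation of prohibited drugs". The table below it gives each drug's half-life, its QT association and status, and possible washout periods in hours or days.

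- **Amiodarone** is marked strong association, prohibited. The half-life cell reads "58 days (15-142) 36 days (active metabolite"), and the days column gives 180.
- **Pimozide** is also prohibited. Its half-life is 55 hours and its washout 10 days.
- **Levomethadyl**, another prohibited drug with several species, lists "2.6 day for LAAM, 2 day for nor-LAAM, 4 day for dinor-LAAM" and a washout of 20 days.

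Exclusion 3.2.6 is what brings a site to this table: "Condition requiring concurrent use of drugs or biologics with pro-arrhythmic potential (see Appendix F"). The appendix closes with a disclaimer that the chart may be incomplete, adding "Prescribers are advised to do further research if they have additional questions". Nothing in the appendix says which species, or which point of a half-life range, the five half-lives refer to.

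**The concern.** For amiodarone, the rule and the table entry cannot both hold if the rule is applied to the drug that was stopped. The entry matches five half-lives of the shorter-lived species, while the parent has had little more than three. A site is likely to take the number from the column rather than recompute it. It could then start cediranib 110 days earlier than the appendix's own sentence would allow for the parent drug.

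A washout period is a decision threshold, so an internal conflict here matters more than a slip in background text. What is at stake is QT safety in a patient who has recently stopped a strongly QT-prolonging drug. There is a lesser second reason for care. Appendix D lists amiodarone as a moderate CYP3A4 inhibitor to be avoided if possible, and Section 5.4 names CYP3A4 as the principal enzyme forming olaparib's three main metabolites.

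**Working it through.** **Inputs, all from Appendix F.** Rule: 5 half-lives. Amiodarone: parent 58 days (range 15 to 142), active metabolite 36 days, listed washout 180 days. Pimozide: 55 h, listed washout 10 days = 240 h. Levomethadyl: longest-lived species 4 days, listed washout 20 days.

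**Formulas.** Required washout = 5 x half-life. Half-lives covered = listed washout / half-life. Fraction remaining = 0.5^(half-lives covered), assuming first-order elimination. At exactly five half-lives this is 0.5^5 = 3.1%.

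**Reproducing the listed figure.** 5 x 36 = 180 days. The entry reproduces exactly from the metabolite half-life.

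**Amiodarone, parent drug.**
- Required: 5 x 58 = 290 days.
- Shortfall: 290 - 180 = 110 days, and 110/290 = 38%.
- Covered: 180/58 = 3.10 half-lives.
- Remaining: 0.5^3.10 = 11.6%, against 3.1% under the rule.
- Break-even: 180/5 = 36 days. The entry meets the rule only if the parent half-life is 36 days or less.
- Over the row's own range the rule needs 5 x 15 = 75 to 5 x 142 = 710 days. At the 142-day extreme, 180/142 = 1.27 half-lives and 41.5% remains. That is the end of the range, not a typical patient.

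**Pimozide.**
- Required: 5 x 55 = 275 h = 11.5 days.
- Shortfall: 275 - 240 = 35 h, and 35/275 = 12.7%.
- Covered: 240/55 = 4.36 half-lives, leaving 4.9%.

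**Other prohibited rows with a point half-life and a washout.**
- Seven meet the rule: bepridil (210 h needed, 240 h listed), chlorpromazine (150 v 168 h), disopyramide (33.5 v 36 h), haloperidol (90 v 120 h), ibutilide (30 v 36 h), pentamidine (32 v 36 h) and sotalol (60 v 72 h).
- Three miss by rounding only: droperidol (11 v 10 h), dofetilide (50 v 48 h) and sparfloxacin (100 v 96 h).
- Levomethadyl meets it on its longest-lived species: 5 x 4 = 20 days.

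Rows that give only a range are left out, because the answer depends on which end is used.

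**The case against.** The best defence is that the operative instruction is the sentence, and the sentence is sound. The columns are headed as possible periods and require nothing. A site that applies the rule itself computes the right answer. The listed 180 days is also five half-lives of a species that the row names, and the rule does not say which species to use.

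The table shows no uniform convention either. Levomethadyl's longest-lived species is itself a metabolite, so that row does not distinguish using the longest-lived species from using the metabolite. Risperidone, which is not prohibited and so not bound by the rule, lists 96 h: close to 5 x 20 h for the parent and short of 5 x 21 to 30 h = 105 to 150 h for its metabolite.

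Part of this stands. The appendix leaves the species open, levomethadyl is weak evidence of intent, and 290 days is not the only defensible number. At the 142-day extreme even 290 days covers only 290/142 = 2.04 half-lives.

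What does not stand is the conclusion that there is no conflict. The discontinued drug is amiodarone, and five half-lives have not elapsed while the parent has had 3.1. Pimozide lists a single half-life and still falls short. Neither the column heading nor the disclaimer says which prevails when number and rule disagree.

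The practical objection is stronger. Exclusion 3.2.6 addresses concurrent use and states no washout itself. It also excludes "Patients with QTc prolongation > 500 msec or other significant ECG abnormality noted within 14 days of treatment", with a 470 msec limit in Phase 1-T. Exclusion 3.2.17 covers "Uncontrolled intercurrent illness including, but not limited to ongoing or active infection, symptomatic congestive heart failure, unstable angina pectoris, cardiac arrhythmia". The Phase II calendar requires "ECG done prior to Cycle 1 and 2, and then prior to every cycle if clinically indicated", and the Phase I calendar does the same. These safeguards limit the consequence considerably.

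**Conclusion.** The point holds as a minor internal inconsistency. Applied to the parent drug at its point half-life, the appendix's own rule gives 290 days for amiodarone, and the listed 180 days is 110 days (38%) short. Pimozide is 35 h (12.7%) short. The residual fractions assume first-order elimination. The 290-day figure assumes that the rule refers to the longest-lived species listed.

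A reader might infer more than the documents support:
- **That 180 days is a plain miscalculation with 290 the only correct value.** It is correct for the metabolite, and the text does not name the species.
- **That the table as a whole is unreliable.** Most prohibited rows with a point half-life meet or exceed the rule, and three of the five that do not are rounding.
- **That patients were put at risk.** The documents do not show that any candidate was in amiodarone or pimozide washout, and the QTc limits, ECGs and arrhythmia exclusion apply regardless.

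Endpoints, power and analysis are unaffected.

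**What to change.** Change the amiodarone washout to 290 days and the pimozide washout to 12 days. Add to the opening sentence of Appendix F that the 5 half-life rule, applied to the longest-lived listed species, prevails wherever it is longer than the Possible Washout Period entry. With that sentence in place, droperidol, dofetilide and sparfloxacin need no row edits.

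One gap would remain. Rows that give only a range still need a stated choice of which end to use. Cisapride shows why: 60 h is listed, which is 5 x 12 h, but 5 x 20 h = 100 h at its listed upper value. The sponsor should settle this in the same sentence.

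The cost is one sentence and two table entries, with no change to sample size or analysis. The downside is that a rare candidate waits longer: up to 110 days more after amiodarone and 2 days more after pimozide.

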1. INTRODUCTION

The Dana-Farber/Harvard Cancer Center Multi-Center Data and Safety Monitoring Plan (DF/HCC DSMP) outlines the procedures for a DF/HCC Multi-Center research protocol.

1.1 Purpose

To establish standards that will ensure that a Dana-Farber/Harvard Cancer Center (DF/HCC) Multi-center protocol will comply with Federal regulations (21 CFR Part 11); Good Clinical Practice (GCP) Guidelines; and Health Insurance Portability and Accountability Act (HIPAA) requirements in accordance with the CTEP Multi-center Guidelines.

1.2 Multi-Center Data and Safety Monitoring Plan Components

The Multi-Center Data and Safety Monitoring Plan includes the following components:

DF/HCC Multi-center Protocol: One or more outside institutions collaborating with Dana-Farber/Harvard Cancer Center on a research protocol where DF/HCC is the Lead Institution. Dana-Farber/Partners Cancer Care (DF/PCC) Network Clinical Trial Affiliates are not viewed as outside sites in this definition.

Lead Institution: One of the Dana-Farber/Harvard Cancer Center sites (DFCI, MGH, BIDMC, CH, BWH) will be the Lead Institution and will be responsible for the coordination, development, submission, and approval of a protocol as well as its subsequent amendments per the DFCI IRB and applicable regulatory guidelines (CTEP, FDA, OBA etc.).

DF/HCC Contract Principal Investigator: Investigator located at the Lead Institution who will be charged with the responsibility of the administration of the DF/HCC Project. This most often will be the Protocol Chair, but occasionally this may be the overall grant or contract holder, as applicable.

Protocol Chair: The Protocol Chair is the Principal Investigator for the DF/HCC protocol submitted as the Lead Institution. For applicable protocols, the Protocol Chair will be the single liaison with any regulatory agencies (i.e. CTEP Protocol and Information Office (PIO), FDA, OBA etc.).

Participating Institution: A participating institution is an institution that desires to collaborate with DF/HCC and commits to accruing participants to a DF/HCC protocol. The participating institution acknowledges the Protocol Chair as having the ultimate authority and responsibility for the overall conduct of the study.

Coordinating Center: The Lead Institution is the Coordinating Center for the DF/HCC Multi-center Protocol. The Coordinating Center will provide the administrative support to the Protocol Chair in order that he/she may fulfill the responsibilities outlined in the DSMP and as specified in applicable regulatory guidelines (i.e. CTEP Multi-Center Guidelines). In addition to the Lead Institution, the Quality Assurance Office for Clinical Trials (QACT) provides support services to

assist the Protocol Chair.

